## **1 INTRODUCTION**

The purpose of this document is to give details for the statistical analysis of study D9487C00001 (DALIZE-Outcomes), supporting the clinical study report. The details of study conduct and data collection are provided in the clinical study protocol (CSP) and the case report form (CRF).

## **2 CHANGES TO PROTOCOL PLANNED ANALYSES**

There are no changes to protocol planned analyses. However, safety analysis dataset was renamed as safety set (SS).

## **3 DATA ANALYSIS CONSIDERATIONS**

### **3.1 Timing of Analyses**

The study involves two interim analyses (the first interim analysis is for futility and the second interim analysis is for efficacy) and the final analysis.

Thus, there are three timepoints for planned analyses in the study: one corresponding to study completion, planned to take place when 730 subjects had an adjudicated primary composite event, and the other two corresponding to interim analyses planned to take place when 292 (40% information fraction) and 511 (70% information fraction) subjects, respectively had an adjudicated primary composite event. The interim analyses will be conducted by independent data monitoring committee (DMC) and will mainly be aimed at evaluating the primary objective of the study with the possibility of early stopping for either futility (at n=292 events) and for efficacy (at n=511 events). In case of an early stopping of the study at efficacy interim analyses, all analyses as specified in this document will be conducted. However, if the study stops for futility, only selected analyses covering key efficacy and safety outcomes will be conducted.

### **3.2 Analysis Populations**

Two analysis sets are defined according to International Conference on Harmonization (ICH) E9 guideline.

Full analysis set (FAS) includes all subjects who underwent randomization and received a randomization number, irrespective of their protocol adherence and continued participation in the study. Subjects will be analysed according to their randomized study intervention assignment, irrespective of the treatment actually received. The FAS will be used as the analysis set for all efficacy analyses.

Safety Set (SS) includes all subjects who are randomised and have received at least one dose of study intervention (SZC or Placebo). Subjects will be analysed according to the treatment randomised. The SS will be used as the analysis set for all safety analyses.

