**Table 8 Populations for Analysis**

Population/Analysis Set	Description
Full Analysis Set (FAS)	All participants who undergo randomization and receive a randomization number
Safety Analysis Set (SAS)	All participants who have received at least one dose of study intervention

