## **B 4 Medication Error, Drug Abuse, and Drug Misuse**

### **Medication Error**

For the purposes of this clinical study a medication error is an unintended failure or mistake in the treatment process for an AstraZeneca study intervention that either causes harm to the participant or has the potential to cause harm to the participant.

A medication error is not lack of efficacy of the drug, but rather a human or process related failure while the drug is in control of the study site staff or participant.

Medication error includes situations where an error:

- Occurred
- **Was identified and** intercepted before the participant received the drug
- Did not occur, but circumstances were recognized that could have led to an error

Examples of events to be reported in clinical studies as medication errors:

- Drug name confusion
- Dispensing error, eg, medication prepared incorrectly, even if it was not actually given to the participant
- Drug not administered as indicated, for example, wrong route or wrong site of administration
- Drug not taken as indicated, eg, tablet dissolved in water when it should be taken as a solid tablet
- Drug not stored as instructed, eg, kept in the refrigerator when it should be at room temperature

- Wrong participant received the medication (excluding Interactive Response Technology [IRT]/Randomization and Trial Supply Management [RTSM] errors)
- Wrong drug administered to participant (excluding IRT/RTSM errors)

Examples of events that **do not** require reporting as medication errors in clinical studies:

- Errors related to or resulting from IRT/RTSM - including those which lead to one of the above listed events that would otherwise have been a medication error
- Participant accidentally missed drug dose(s), eg, forgot to take medication
- Accidental overdose (will be captured as an overdose)
- Participant failed to return unused medication or empty packaging
- Errors related to background and rescue medication, or standard of care medication in open-label studies, even if an AstraZeneca product.

Medication errors are not regarded as AEs, but AEs may occur as a consequence of the medication error.

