#### **3.4.4 Handling of Protocol Deviations in Study Analysis**

The section covers the list of potential Important Protocol Deviations (IPDs) that might potentially impact the results of the analyses and/or are a serious breach of Good Clinical Practice (GCP).

The IPDs will be categorized as follows:

1. Written informed consent not obtained prior to mandatory study specific procedures, sampling and analyses.
2. Received alternative protocol specific therapy than that which they were randomised.
3. Developed discontinuation of study intervention criteria during the study, but remained on the study intervention.
4. Site procedure for unblinding of the subject is not complaint with the CSP.
5. Received prohibited/excluded concomitant medication.

As the main efficacy analyses for the study follow the intention-to-treat principle, presence of protocol deviations for a subject will not imply exclusion of the subject, or any data obtained from the subject, from these analyses. However, supplementary analyses aimed at e.g., evaluating potential efficacy for subjects who remain on the assigned study treatment regimen might be conducted. As such analyses are per protocol in nature, they would exclude data obtained following a protocol deviation, see Section 4.2.

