### **Listings**

The listings provided will include, but may not be limited to:

- All AE
- All AE of hypokalemia. The listing will e.g. include information on the actual SK value observed during the AE.
- SAE for enrolled, but not randomized, subjects.

All listings will be created for during the study time period, and will include planned treatment arm, actual treatment arm, planned dose, actual dose and time since the actual last IP administration date.

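### The Safety Set is analysed by randomised arm, so sustained use of the other product would bias the safety tables toward no difference; the expected effect is very small

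*SAP*

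**What the plan says.** SAP 3.2 admits a participant to the Safety Set on randomisation plus at least one dose of either product, and then sets the arm rule: "Subjects will be analysed according to the treatment randomised". The scope is complete: "The SS will be used as the analysis set for all safety analyses". The rule for the Full Analysis Set is the same in substance: "Subjects will be analysed according to their randomized study intervention assignment, irrespective of the treatment actually received".

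The protocol has no arm rule for safety. Its Table 8 defines the set only by exposure ("All participants who have received at least one dose of study intervention"), and Section 9.4.3 adds nothing on this point. The SAP sentence is therefore the only rule.

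Both documents allow for receipt of the wrong product. SAP 3.4.4 has an important protocol deviation category for it ("Received alternative protocol specific therapy than that which they were randomised"), and protocol Appendix B 4 lists administration of the wrong drug among reportable medication errors, apart from errors of the interactive response system. The adverse event listings in SAP 4.5.1.2 "will include planned treatment arm, actual treatment arm", together with planned and actual dose.

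**The concern.** For efficacy, analysis by randomised arm preserves the randomised comparison, and any dilution works against the drug. Protocol Section 3 makes that argument when it calls the treatment policy approach conservative. For safety the same dilution works in the drug's favour. Hypokalaemia and oedema-related events are the identified risks of SZC (protocol 2.3) and are events of special interest in SAP 4.5.1.2. Under the current rule, such an event in a placebo-randomised participant who was in fact taking SZC is tabulated as a placebo event.

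The planned tables do not separate this out. The supportive on-treatment tables (SAP 3.4.1.4 and 4.5) change the time window and leave the arm as randomised, so a participant on the wrong product is shown as on treatment with a product they were not taking. Actual treatment is specified for the listings only.

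**Working it through.** The plan states no figure on this point, so there is none to reproduce. The check is a comparison of the rules above plus an illustration of size.

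**Inputs from the documents.** About 2800 participants randomised 1:1, so about 1400 per arm (SAP 3.3). Average treatment about 37 months (SAP 3.3). Dispensing weekly for four dispensations and every four weeks thereafter (protocol 6.1.2).

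**Inputs assumed, because the documents give none.** The share m of each arm on the other product, taken as 0.1% to 5%. True event risks of 10% on SZC and 5% on placebo, for illustration only.

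**Case 1: other product taken throughout.** Let p_S and p_P be the true risks on SZC and placebo. By randomised arm:

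- SZC arm: (1 - m) p_S + m p_P
- Placebo arm: (1 - m) p_P + m p_S
- Difference: (1 - 2m)(p_S - p_P)

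If the shares differ, a in the SZC arm and b in the placebo arm, the factor is 1 - a - b. A one-way error therefore also attenuates.

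| m | Shrinkage, 2m | Risk difference, points | Risk ratio | SZC-exposed participants with an event counted under placebo (1400 × m × 0.10) |
|---|---|---|---|---|
| 0 | 0 | 5.00 | 2.000 | 0 |
| 0.1% | 0.2% | 4.99 | 1.997 | 0.14 |
| 1% | 2% | 4.90 | 1.970 | 1.4 |
| 5% | 10% | 4.50 | 1.857 | 7 |

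For scale, the standard error of the risk difference is √[(0.10 × 0.90 + 0.05 × 0.95)/1400] = √(0.1375/1400) = 0.0099, or about 1.0 point. At m = 1% the bias of 0.10 point is about a tenth of that.

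**Case 2: one wrong four-week supply.** At 30.4 days per month, 37 months is 37 × 30.4 = 1125 days, and 1125/28 is about 40 four-week intervals. If a share m of each arm had one wrong supply, the misallocated share of exposure is m/40. Under constant event rates the shrinkage is about 2m/40:

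- m = 1%: 2 × 0.01/40 = 0.0005, or 0.05%
- m = 3%: 2 × 0.03/40 = 0.0015, or 0.15%

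That is 40 times smaller than in Case 1 at the same m. Only sustained misallocation could matter.

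**The case against.** The strongest case for leaving the rule alone is that it is a disclosed choice with almost no effect. SAP 4.5 says that the main safety presentation follows the intention-to-treat approach used for efficacy, the protocol sets no arm rule to contradict, and analysis by randomised arm keeps the randomised comparison. Safety is descriptive, so no test or decision depends on it. Cases would not be hidden either: deviation categories, including wrong therapy, are counted by arm (SAP 4.1 and 4.1.3.2), and the listings let a reader trace each event. If no one receives the wrong product, the two rules give identical tables.

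Most of this stands, and it limits the point. One part does not. SAP 4.5 attaches the intention-to-treat rationale to the follow-up period, not to the choice of arm, and that rationale loses its conservative character when the outcome is harm. Traceability also falls short of a summary by treatment received.

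Three stronger readings are tempting and are not supported:

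- A reader might infer that the plan expects participants to receive the wrong product. SAP 3.4.4 lists potential deviations, which is not a forecast.
- A reader might take shrinkage of 2% or more as the likely size. That needs the other product to be taken throughout, and the documents give no rate at all.
- A reader might see a departure from the protocol. The protocol is silent on the arm rule.

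**Conclusion.** The concern holds as a minor improvement. By rule, a participant who takes the other product for all or most of the exposure has their adverse events reported under the wrong product. The direction is toward no difference, which for safety is the unfavourable direction, and no planned summary table shows the result by treatment received.

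The size is very small. The factor 1 - 2m rests on assumed shares m, equal in both arms and sustained throughout; isolated wrong dispensations have a negligible effect. The case for change rests on direction and interpretability at almost no cost, not on an expected material bias.

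**What to change.** In SAP 3.2, replace the Safety Set arm sentence with:

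> Subjects in the SS will be analysed according to the treatment actually received; a subject who received both products is analysed under the product taken for the majority of the exposure, and all subjects with any wrong-product exposure are listed.

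Keep the Full Analysis Set as randomised. Make the change before unblinding.

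A rule that moves anyone with any SZC exposure to the SZC arm should not be used. For a placebo participant given one wrong kit it could transfer about three years of placebo follow-up to SZC, a larger misattribution than the one being corrected. The majority rule leaves that participant under placebo, as now, and acts only when misallocation is sustained.

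The cost is one sentence. Actual treatment arm is already required for the listings, so no new data are needed. The downside is that a few participants may leave their randomised group in the safety tables, so those tables would no longer be a strictly randomised comparison. The change covers study product only; non-protocolised SZC, which SAP 4.2.1.6 addresses for efficacy, is a separate route of exposure and is not affected.

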### **3.3 Sample Size Determination**

The study is event-driven. The primary objective of the study is to evaluate the efficacy of SZC versus placebo in reducing the incidence of the primary composite endpoint.

Assuming the true HR for SZC versus placebo is 0.8, 730 primary endpoint events will result in 84.7% statistical power to demonstrate a statistically significant difference at either second interim analysis using two-sided significance level of 1.64% or at the final analysis using two-sided significance level of 4.46%. Based on an assumption that the event rate of the primary composite endpoint is approximately 0.11 per patient-year in the placebo group, it is expected that approximately 2800 participants will need to be randomized. The anticipated recruitment period is planned to be 32 months. The anticipated average treatment period is approximately 37 months, which in practice will be dependent on the actual event rate observed during the study, as the study duration is event driven. Any decision to increase or decrease participant numbers will be based on blinded event rate data (e.g., observed overall event rate), and study discontinuation rate.

Assuming a screen failure rate of 50%, approximately 5600 participants will be enrolled to achieve approximately 2800 participants randomly assigned (1:1) to study intervention (SZC or placebo).

### **3.4 General Considerations**

In order to provide an overview of the data, descriptive statistics will be utilized. The type of descriptive statistic will depend on the variable being summarized, with number of patients with available data (n), mean, standard deviation, median, quartiles, minimum, and maximum used to summarize continuous variables, and counts and percentages used to summarize categorical variables.

Missing data will be ignored in the descriptive statistical summaries, and only subjects with non-missing data at the relevant timepoint will be included. For the percentage calculation for the categorical variables, the number of subjects randomized to each of the treatment arms, as well as the total number of subjects in the relevant study population (e.g FAS), will be used as a rule, unless otherwise specified in the detailed analyses descriptions given below.

Kaplan-Meier estimates will be used to illustrate the distribution of time-to-event data. If Cox regressions are used for a more formal time to event analysis, no hazard ratio estimates with confidence interval and p-values will be given when less than 15 events in total are observed during the relevant time period, both treatment groups combined.

All of analyses will be conducted by AstraZeneca using SAS version 9.4 or higher.

### **3.4.1 General Study Level Definitions**

#### **3.4.1.1 Study End Date (SED)**

The executive committee and AstraZeneca will monitor the accrual of endpoint events and, when appropriate, define the study end date as the date at which the pre-defined target number of 730 subjects are expected to have experienced a primary adjudicated event. The SED will be used as a global censoring time point for all main time to event analyses performed for the study. However, if the study is stopped before the planned stop date (e.g. based on the results of interim analyses), then the SED will be determined as per early stopping decision.

#### **3.4.1.2 Withdrawal of consent (WoC)**

Withdrawal of consent (WoC) refers to the date when the patient withdrew their consent for participation in the study.

#### **3.4.1.3 Lost to follow-up (LTFU)**

Lost to follow-up (LTFU) refers to the last date of contact with the patient if the contact with the patient was lost during the course of the study.

#### **3.4.1.4 During the study and on-treatment definitions**

For every patient, the following definitions will be used in safety analyses.

##### **During the study**

“During the study” is defined as time from the randomization day to the date of last contact or death.

##### **On-treatment**

“On-treatment” is defined as the period between the first day of planned intake of study intervention to one day after the day of the last actual dose of study intervention.

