## 4 STUDY DESIGN

### 4.1 Overall Design

This is an international, multicenter, event-driven, randomized, double-blind, parallel group, placebo-controlled study, evaluating the utility of SZC versus placebo to reduce the incidence

of SCD, stroke, and arrhythmia-related hospitalizations, interventions, and ED visits in participants on chronic hemodialysis with recurrent hyperkalemia.

It is estimated that approximately 5600 participants at about 330 study sites in about 26 countries will be enrolled to reach the target of 2800 participants randomized (1:1) to study intervention (SZC or placebo).

The study design will consist of the following planned phases:

- Screening phase (2 to 6 weeks; no study intervention administered). Data required for determination of eligibility are collected and inclusion/exclusion criteria are evaluated.
- Randomized (1:1 ratio) treatment phase (on study intervention until required number of events are accrued). The dose of study intervention will be up-titrated weekly in 5 g increments starting at 5 g qd on non-dialysis days (4 doses per week) based on local laboratory pre-dialysis S-K values to achieve and maintain a pre-dialysis S-K between 4.0 and 5.0 mmol/L after the LIDI. The maximum dose of study intervention will be 15 g qd on non-dialysis days. After the initial up-titration, monthly (or more frequent based on clinical judgment) pre-dialysis S-K will be collected after the LIDI at the local laboratory to guide further dose adjustment at any time during the study to achieve and maintain a pre-dialysis S-K between 4.0 to 5.0 mmol/L.

This study is event-driven. The study closure procedures will be initiated when the predetermined number of primary endpoint events are expected to have occurred (730 events). The anticipated recruitment period is planned to be 32 months. The anticipated average treatment period is approximately 37 months, which in practice will be dependent on the actual event rate observed during the study, as the study duration is event-driven. The study duration may be changed if the number of participants enrolled, the event rate, or the randomization rate is different than anticipated. Any decision to increase or decrease participant numbers or extend or shorten the study duration will be based on blinded event rate data.

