#### **Type of Participant and Disease Characteristics**

- 4 Receiving hemodialysis (or hemodiafiltration) 3 times a week for treatment of ESRD for  $\geq$  4 months before enrollment

- 5 Must have hemodialysis access consisting of an arteriovenous fistula, arteriovenous graft, or tunneled (permanent) catheter which is expected to remain in place for the entire duration of the study
- 6 At least 2 out of 2 or 2 out of 3 pre-dialysis S-K values  $\geq 5.5$  mmol/L after the LIDI during screening

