### 6.1.2 Dose and Treatment Regimens

SZC or placebo will be suspended in 45 ml of water and administered orally on non-dialysis days.

For participants on dialysis, study intervention should only be dosed on non-dialysis days. The recommended starting dose is 5 g once daily. To establish normokalaemia (4.0 to 5.0 mmol/L based on local laboratory pre-dialysis S-K values), the dose should be titrated weekly based on the pre-dialysis serum potassium value after the LIDI.

The dose should be adjusted at intervals of 1 week in increments of 5 g up to 15 g once daily on non-dialysis days. In case of dose adjustment serum potassium must be measured one week after the dosage change. After the initial titration and once normokalaemia is established, potassium should be monitored regularly (eg, monthly, or more frequently based on clinical judgment including changes in dietary potassium or medication affecting serum potassium).

Once normokalaemia is established, pre-dialysis S-K will be collected after the LIDI at the local laboratory and the study intervention dose adjusted depending on the current potassium value to achieve and maintain a pre-dialysis S-K between 4.0 to 5.0 mmol/L. The maximum dose of study intervention will be 15 g qd on non-dialysis days.

Study intervention will be dispensed to the participant at the time of the dose adjustment review: weekly for 4 dispensations and every 4 weeks thereafter. Study intervention may be dispensed more frequently if needed (eg, if the participant's dose is changed per dose adjustment review). The Study Events questionnaire will be administered at each dispensation visit and followed by an investigator follow-up/phone visit, if needed (refer to [Table 2](#) and [Appendix B 5](#)). Compliance reminders and accountability checks will also be performed at every dispensation (Sections [6.2](#) and [6.4](#)).

Rescue therapy should be guided by local clinical practice patterns. Rescue therapy should be followed by the appropriate dose adjustment if appropriate and proper documentation of the event (Section [6.5.2](#)).

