#### **4.5.1.2 Presentation**

##### **Overall overview**

An AE overview table will be created, with AEs falling within the following categories summarized by treatment group.

- Any AE
- Any SAE
- Any AE with outcome death
- Any AE leading to discontinuation of IP
- Any AE possibly related to IP
- Any event of hypokalaemia
- Any event of hyperkalemia requiring rescue therapy

This summary will be replicated for on-treatment analysis period.

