##### **AEs, SAEs, DAEs and deaths, by system organ class and preferred term**

A detailed overview of number, and percentage, of subjects with AEs, SAEs, DAEs and deaths in a particular SOC and PT class will be presented. In addition, for AEs and SAEs, a corresponding overview of the number of AEs in a particular SOC/PT class, and the rate of AEs, will be created.

The summaries of SAEs and DAEs will be replicated for on-treatment analysis period.

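### The SAP's one-day on-treatment tail is shorter than the regular two-day dose interval, so some dosing-ending events in fully adherent participants count as off-treatment in supportive safety tables

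*SAP*

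**What the plan says.** SAP 3.4.1.4 defines two periods and states that "the following definitions will be used in safety analyses". The on-treatment period starts on the first day of planned intake and closes "one day after the day of the last actual dose of study intervention". In calendar days, the day of the last dose (day 0) and the next day (day +1) are inside, and day +2 is outside.

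The regimen is intermittent:

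- Protocol 5.1, criterion 4: "Receiving hemodialysis (or hemodiafiltration) 3 times a week for treatment of ESRD".
- Protocol 6.1.2: "study intervention should only be dosed on non-dialysis days".
- Protocol 4.1 gives the weekly count: "starting at 5 g qd on non-dialysis days (4 doses per week".

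SAP 4.5 makes the *during the study* period primary for safety and treats the on-treatment tables as supportive. In SAP 4.5.1.2 the AE overview has lines for AEs with a fatal outcome and AEs leading to discontinuation, and "This summary will be replicated for on-treatment analysis period". For the tables by system organ class, "The summaries of SAEs and DAEs will be replicated for on-treatment analysis period". The common-AE, oedema and potassium-event tables (4.5.1.2) and the laboratory and vital-sign abnormality tables (4.5.2.2) are also repeated on-treatment.

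Neither document gives a reason for one day. SAP 3.4.1.4 does not say whether onset, death or discontinuation date decides the class of an event.

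**The concern.** A one-day tail fits a drug taken every day: an adherent participant is then never more than one day from the last dose. Here an adherent participant is regularly two days from it. If an event on such a day prevents the next dose, the last actual dose stays two days back and the event falls outside the window.

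Only events that end dosing for good can be lost in this way. If dosing resumes, the window runs on to the later final dose and the event stays inside. What can drop out is therefore a death, or an AE that stops the drug at once, and these are events that an on-treatment summary is meant to show. An AE that caused discontinuation could be absent from the on-treatment table of such AEs. Potential endpoints are also reported as AEs (Protocol 8.1.1 and 8.3), so sudden cardiac deaths come under the rule.

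**Working it through.** **Inputs.** Three dialysis sessions a week (Protocol 5.1); dosing on non-dialysis days only (6.1.2); window to day +1 (SAP 3.4.1.4). Assumptions: dialysis days are not consecutive, as a single long interdialytic interval implies; adherence is full; the last-dose date is accurate; AEs are classified by onset. The clock hour of dosing, h, is not in the documents and is varied.

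**Step 1: reproduce the plan's figure.** 7 − 3 = 4 doses per week, as Protocol 4.1 states.

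**Step 2: dose intervals.** With Mon/Wed/Fri dialysis, doses fall on Tue, Thu, Sat and Sun. The intervals are Tue–Thu 2 days, Thu–Sat 2, Sat–Sun 1 and Sun–Tue 2, so three of four are two days. Each two-day interval contains one dose-free day, the dialysis day.

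**Step 3: days since last dose, before any dose that day.**

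| Day | Type | Last dose | Lag | Inside +1? |
|---|---|---|---|---|
| Mon | dialysis | Sun | 1 | yes |
| Tue | dosing | Sun | 2 | no, until dosed |
| Wed | dialysis | Tue | 1 | yes |
| Thu | dosing | Tue | 2 | no, until dosed |
| Fri | dialysis | Thu | 1 | yes |
| Sat | dosing | Thu | 2 | no, until dosed |
| Sun | dosing | Sat | 1 | yes |

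All three dialysis days are covered, including Monday at the end of the long interval. The uncovered time runs from midnight to the dose on Tue, Thu and Sat. Tue/Thu/Sat dialysis gives the same pattern on shifted days.

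**Step 4: share of the week.** Uncovered share = 3h/168, or 3p/7 with p = h/24.

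| Dosing hour | 3h/168 | Share |
|---|---|---|
| 06:00 | 18/168 | 10.7% |
| 08:00 | 24/168 | 14.3% |
| 12:00 | 36/168 | 21.4% |
| 18:00 | 54/168 | 32.1% |
| 24:00 (ceiling) | 72/168 | 42.9% |

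This equals the share of dosing-ending events misclassified only if those events are spread evenly over the week.

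**Step 5: window to day +2.** The largest lag in Step 3 is 2, so the uncovered share on the regular schedule is 0/168 = 0% at any dosing hour.

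**Step 6: irregular weeks.** Suppose an extra session on Thursday, with no dose that day. Doses are then Tue, Sat and Sun, with intervals of 4, 1 and 2 days. Even with day +2 included, Friday (lag 3) and Saturday before the dose (lag 4) are outside: (24 + h)/168, or 36/168 = 21.4% of that week for noon dosing.

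**The case against.** The strongest reply is that nothing is hidden. The primary tables count every death, SAE and drug-stopping AE whatever the dose timing. SAP 4.5.1.2 provides key subject information for SAEs, fatal AEs and AEs leading to discontinuation, and the duration variables in 4.5.1.1 include time from last dose to AE start and to death. All AE listings carry time since last administration. A careful reader could find an event at day +2. This stands, and it limits the consequence. It does not correct the counts in the on-treatment tables.

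A reader might infer that fatal or drug-stopping events in adherent participants generally fall off-treatment. They do not: for dosing between 06:00 and 18:00 and an even spread, about 68% to 89% of them stay inside. A drug-stopping AE that began before the last dose also stays inside if onset date is used.

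A reader might also infer that the rule picks out the arrhythmic events this trial studies. The documents do not support that. Protocol 2.2 places raised risk during dialysis, at the end of the long interval and in the 12 hours after a session. Dialysis days and the end of the long interval are covered, which would make the even-spread figures too high for these events. Against that, the 12 hours after a late session could run past midnight into uncovered time, and session times are not given. The direction of the error is unknown.

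Finally, SZC acts locally and is not absorbed (Protocol 2), and the documents give no duration of effect. So it is not shown that day +2 is pharmacologically exposed time. The argument for two days rests on the regimen: a participant who has missed no dose should not be classed as off treatment.

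**Conclusion.** The point holds in a narrow form. Followed as written, SAP 3.4.1.4 classes as off-treatment a death or new AE that ends dosing for good in a fully adherent participant, if it occurs before the dose on a dosing day that follows a dialysis day. Under an even spread of such events and the regular schedule, the share is 11% to 32% for dosing between 06:00 and 18:00, with a ceiling of 43%. The true share cannot be derived from the documents. As a fraction of all events in the on-treatment tables it will be smaller, because events followed by further dosing are unaffected.

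The effect is confined to supportive on-treatment outputs. It would be wrong to read it as touching a separate on-treatment deaths table: SAP 4.5.1.2 repeats the SAE and discontinuation summaries, not the deaths summary, so deaths appear through the AE overview and among SAEs. Nor does it touch efficacy, since the definition is for safety analyses only. The rule is the same in both arms. This is an inexpensive improvement to a definition and no threat to the trial's main conclusions.

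**What to change.** In SAP 3.4.1.4, end the on-treatment period on the second calendar day after the last actual dose, and give the reason: two days is the longest regular interval under the regimen. State that AEs are classified by onset date. Apply the same definition to all on-treatment AE, laboratory and vital-sign tabulations.

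The cost is a sentence or two in the SAP and one constant in the programs. The downside is that up to one more day after the last dose counts as on-treatment for each participant, under the same rule in both arms. The change does not fully cover intervals lengthened by an extra dialysis session or by the hold on study drug during rescue therapy (Protocol 6.5.2). The SAP should say so, and the time-since-last-dose column in the listings will show those cases.
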